### 10.7.3 HANDLING OF ADVERSE EVENTS

---

All adverse events resulting in discontinuation from the trial should be followed until resolution or stabilization. Subjects must be followed for AEs for 30 calendar days after discontinuation or completion of protocol-specific treatment. All new AEs occurring during this period must be reported and followed until resolution unless, in the opinion of the investigator, these values are not likely to improve because of the underlying disease. In this case, the investigators must record his or her reasoning for this decision in the patient’s medical record and as a comment on the CRF. After 30 days, only AEs, SAEs, or deaths assessed by the investigator as treatment related are to be reported.

**MS Relapses during the study:** For subjects having MS disease activity including relapses (protocol defined or otherwise):

Any patient experiencing a multiple sclerosis relapse while on study will be allowed rescue therapy with intravenous methylprednisolone 1gm/day for up to 5 consecutive days. Subjects requiring rescue therapy will have an MRI scan 10 days after completion of treatment with steroids.

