### 3.3 DISCONTINUATION FROM TRIAL TREATMENT

---

Subjects will be discontinued from trial treatment for any of the following reasons:

- Disease progression, defined as 6 month confirmed disability progression ( $\geq 1$  point increase in the EDSS score)
- Irreversible or intolerable toxicity or abnormal laboratory values thought to be related to drug toxicity
- Patient requests to withdraw consent or discontinue treatment
- Pregnancy (see Section 3.3.1)
- Inability of the patient to comply with trial requirements
- Conditions requiring therapeutic intervention not permitted by the protocol
- Inter-current illness (this will be at the investigator's discretion)
- Non-compliance/lost to follow-up
- Discontinuation of the study by the Sponsor

If a patient withdraws from treatment during the first 4 weeks due to any reason other than DLT, that patient will be replaced.

After withdrawal from protocol treatment, subjects must be followed for AEs for 30 calendar days after their last dose of the trial drug. All new AEs occurring during this period must be reported and followed until resolution, unless, in the opinion of the investigator, these values are not likely to improve because of the underlying disease. In this case the investigators must record his or her reasoning for this decision in the subjects' medical records and as a comment on the electronic Case Report Form (eCRF).

All subjects who have CTCAE grade 3 or 4 laboratory abnormalities at the time of withdrawal must be followed until the laboratory values have returned to grade 1 or 2, unless it is, in the opinion of the investigator, not likely that these values are to improve because of the underlying disease. In this case, the investigator must record his or her reasoning for making this decision in the subjects' medical records and as a comment on the eCRF.

---

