### 10.7.1 RECORDING OF ADVERSE EVENTS

---

All adverse events of any patient during the course of the trial will be reported on the case report form, and the investigator will give his or her opinion as to the relationship of the adverse event to trial drug treatment (i.e., whether the event is related or unrelated to trial drug administration –ublituximab). If the adverse event is serious, it should be reported as soon as possible and no greater than 24 hours to the sponsor or designee. Other untoward events occurring in the framework of a clinical trial are also to be recorded as AEs (i.e., AEs that occur prior to assignment of trial treatment that are related to a protocol-mandated intervention, including invasive procedures such as biopsies, medication washout, or no treatment run-in).

All AEs regardless of seriousness or relationship to ublituximab treatment spanning from Day 1 until 30 calendar days after discontinuation or completion of either protocol-specific treatment as defined by the protocol for that patient, are to be recorded on the CRF.

---

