## 10.8.2 SERIOUS ADVERSE EVENT REPORTING BY INVESTIGATORS

---

It is important to distinguish between “serious” and “severe” adverse events, as the terms are not synonymous. Severity is a measure of intensity; however, an AE of severe intensity need not necessarily be considered serious. For example, nausea which persists for several hours may be considered severe nausea, but may not be considered an SAE. On the other hand, a stroke which results in a limited degree of disability may be considered only a mild stroke, but would be considered an SAE. Severity and seriousness should be independently assessed when recording AEs and SAEs on the CRF.

Adverse events classified by the treating investigator as **serious** require expeditious handling and reporting to the Sponsor in order to comply with regulatory requirements. Serious adverse events may occur at any time from the signing of the informed consent form through the 30-day follow-up period after the last trial treatment. Sponsor or designee must be notified of all SAEs, regardless of causality, within 24 hours of the first knowledge of the event by the treating physician or research personnel.

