**To report an SAE, see the appropriate SAE CRF page.**

All SAEs and medically confirmed deaths (regardless of causality assessment) occurring on trial treatment or within 30 days of last trial treatment must be reported to the sponsor as SAEs within the CRF and followed until resolution (with autopsy report if applicable).

Deaths occurring within 30 days after last trial treatment that are deemed ‘possibly’ or ‘probably’ related to ublituximab must be reported as SAEs within the CRF (with an autopsy report if available).

Deaths occurring within 30 days after last trial treatment and not attributed to trial treatment (e.g., disease progression) need not be reported in an expeditious manner to the Sponsor, but can simply be captured on the appropriate CRF as an SAE (death).

The investigator must review and sign off on the SAE data on the SAE report. The SAE will be reported to the Sponsor (or Sponsor designee) as outlined in the Safety Monitoring Plan.

If an SAE is reported to the sponsor or designee via fax, the same information must be entered on the CRF within 24 hours (1 business day). The SAE transmission should be confirmed by the site personnel submitting the report.

Follow-up information for SAEs and information on non-serious AEs that become serious should also be reported to the sponsor or designee as soon as it is available; these reports should be submitted using the appropriate CRF. The detailed SAE reporting process will be provided to the sites in the Safety Monitoring Plan.

Investigators must report SAEs and follow-up information to their responsible Institutional Review Board (IRBs)/Independent Ethics Committee according to the policies of the responsible IRB (Research Ethics Committee).

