### 10.11.3 DEATHS

---

All on-trial deaths, regardless of attribution, will be recorded on an SAE Report Form and expeditiously reported to the Sponsor.

When recording a serious adverse event with an outcome of death, the event or condition that caused or contributed to the fatal outcome should be recorded as the single medical concept on the Adverse Event page of the CRF. If the cause of death is unknown and cannot be ascertained at the time of reporting, record "Death NOS" on the CRF Adverse Event page.

---

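### Protocol 10.7.3 restricts reporting to treatment-related events 30 days after treatment, against text requiring all-causality capture, and the start of the 30 days is inconsistent

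*Protocol*

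**What the plan says.** **Restrictive text.** Protocol 10.7.3 asks for adverse event follow-up for 30 days after treatment is discontinued or completed, and then states: "After 30 days, only AEs, SAEs, or deaths assessed by the investigator as treatment related are to be reported".

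**Full-capture text.**
- Protocol 10.7.1, first sentence: "All adverse events of any patient during the course of the trial will be reported on the case report form".
- Protocol 10.5: AEs and SAEs that occur on study are all to be listed by patient.
- Protocol 10.11.3: "All on-trial deaths, regardless of attribution, will be recorded on an SAE Report Form".
- SAP 2.1.4.1: AEs, SAEs and AESIs are captured from consent until the subject's participation ends.

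The evaluation table (protocol 7) marks adverse events at every visit from Day 1 to W48. It is silent on causality.

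**30-day periods with no related-only rule.**
- Protocol 10.7.1, second paragraph, has all AEs, related or not, recorded "until 30 calendar days after discontinuation or completion of either protocol-specific treatment".
- Protocol 10.8.2 describes SAEs as arising from consent "through the 30-day follow-up period after the last trial treatment", and covers SAEs and deaths "occurring on trial treatment or within 30 days of last trial treatment must be reported to the sponsor as SAEs".
- Protocol 3.3, for withdrawals only: "After withdrawal from protocol treatment, subjects must be followed for AEs for 30 calendar days after their last dose of the trial drug".

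**The concern.** The last infusion is at Week 24 and the study ends at Week 48, so a 30-day clock started at the last infusion expires well inside the study. A site that obeys 10.7.3 on that reading would not report a late infection judged unrelated. A site that follows the opening of 10.7.1 would. The SAP tables treat capture as complete to the end of participation, so a shortfall would not be visible in them.

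The number and severity of infectious AEs is a declared safety endpoint, and the synopsis speaks of safety over the 52-week trial. Late infections are a relevant question here: in the earlier clinical work summarised in protocol 1.2.2.2, lymphocyte depletion lasted about six months from the start of therapy in most subjects.

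**Working it through.** The documents give no figure for this point, so there is none to reproduce. The check has two parts: where the clock starts, and how much follow-up lies beyond it.

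**Start of the 30 days**

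| Start | Where |
|---|---|
| Last dose or last trial treatment | Protocol 3.3 (withdrawals), 10.5 (TEAE definition), 10.8.2 (SAEs, deaths); SAP 2.1.1 also ends the treatment period on the last dosing day when classifying concomitant medication |
| Completion of treatment, not defined | Protocol 10.7.1 and 10.7.3 |
| Treatment lasting 48 weeks | SAP 2.3 (disposition) and SAP 2.4.3 (treatment years run to the Week 48 visit) |

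Protocol 5.4 has treatment continuing past 24 weeks and gives no end.

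**Inputs for the day count**
- Week 24 is Day 168 in the SAP 2.5.3 window table and Day 180 in protocol 7.1.1.
- Week 48 is Day 336 in SAP 2.5.3. On a calendar that puts Week 24 at Day 180, Week 48 is 2 × 180 = Day 360.
- The subject receives all three infusions and is followed to Week 48. Days run from the first ublituximab infusion; for placebo-first subjects the evaluation table restarts there.

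**Formula.** Related-only days = max(0, end − (start of clock + 30)). Share = related-only days / end.

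| Reading | Full reporting until | Related-only days | Share |
|---|---|---|---|
| Clock from Week 24 = Day 168, end Day 336 | 168 + 30 = 198 | 336 − 198 = 138 | 138/336 = 41.1% |
| Clock from Week 24 = Day 180, end Day 360 | 180 + 30 = 210 | 360 − 210 = 150 | 150/360 = 41.7% |
| Clock from Week 48 = Day 336 | 336 + 30 = 366 | 0, since 366 > 336 | 0% |
| Full-capture text governs | end of study | 0 | 0% |

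**Visits.** The AE row covers 17 visits: W1D1, W1D2, W2, W3D15, W4, W8, W12, W16, W20, W24, two days after the W24 dose, W25, W28, W36, W40, W44 and W48. On the SAP calendar W28 is Day 196, or Day 198 at the late edge of its ±2 days, so it is still under full reporting. W36 (252), W40 (280), W44 (308) and W48 (336) come after Day 198: 4 of 17. On the Day 180 calendar, at 7.5 days a week, W28 falls on Day 210, the cut-off itself, and W36 on Day 270, so the same four visits are affected.

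**What could go unreported.** Protocol 10.7 counts Possible, Probable, Definite and missing causality as drug related. Only events judged Not Related or Doubtful are at risk. Infusion-associated AEs (within 24 hours of an infusion), DLTs (first 4 weeks), scheduled laboratory, MRI and relapse assessments, and malignancies (10.11.6, no time limit) are outside the problem.

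**The case against.** The strongest reply is that most of the text already points to full capture. The opening of 10.7.1, 10.5, 10.11.3 and SAP 2.1.4.1 all do, and the TEAE definition names the end of the study as one of its limits. On that view one sentence in 10.7.3 is badly placed and was meant for the time after the study. This may be the intention, but 10.7.3 does not say so, no passage says which text prevails, and its word for the restriction is exclusive.

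Three further points stand, and they limit the finding.

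- **Not every 30-day passage is a contradiction.** A reader might infer that 3.3, 10.7.1 (second paragraph) and 10.8.2 also forbid later reporting. They set periods and prohibit nothing beyond them. They are out of line with full capture, but the explicit restriction is in 10.7.3 alone. For SAEs, a document not provided may settle the matter: "The detailed SAE reporting process will be provided to the sites in the Safety Monitoring Plan".
- **The evaluation table does not settle causality.** It shows that AEs are asked about at W36 to W48, not that unrelated ones must be reported.
- **The consequence is bounded.** Safety analysis is descriptive, and placebo subjects move to active treatment after Day 28, so late counts have no concurrent placebo comparison to distort. The synopsis also opens its safety endpoints by referring to the treatment period, although the same sentence ends with the 52-week trial.

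**Conclusion.** The contradiction holds and should be fixed. A stated rule in 10.7.3 conflicts with four full-capture passages, and its 30-day clock starts at different points in different sections. For a subject with all three infusions followed to Week 48, about 41% of follow-up days and the last four AE visits are related-only if the clock runs from the Week 24 infusion. The share is 0% for completers if treatment runs to Week 48 or the full-capture text governs. Even with a Week 48 completion, 10.8.2 still counts from the last trial treatment and so stays out of line with the SAP.

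Several stronger readings are tempting but not supported.

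- **That 41% of late events are lost.** The figure is a share of days. The loss depends on which text sites followed and how many late events were judged unrelated, and neither is known.
- **That the share could be as low as 126/336 = 37.5%.** This sets Week 24 at Day 180 against Week 48 at Day 336, which mixes two calendars.
- **That early stoppers have a calculable restricted share.** Those who remain under assessment (SAP 2.3; protocol 5.2 and 5.4) would have a longer restricted period, but no visit schedule is given for them, so its length cannot be derived.
- **That the 30-day start is undefined throughout.** Several sections do give one; the fault is inconsistency.

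**What to change.** - State one end point for all-causality collection of AEs, SAEs and deaths: the Week 48 visit (or study withdrawal if earlier) or 30 days after the last infusion, whichever is later.
- Apply the related-only sentence in 10.7.3 only after that point.
- Align 10.7.1, 10.8.2 and 3.3 with it, define completion of treatment, and bring the wording on deaths in 10.7.3 into line with 10.11.3.
- Check the Safety Monitoring Plan against the same end point.
- If sites have already worked under the restrictive text, report AE incidence separately up to and after last dose + 30 days, so that any under-capture can be seen.

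The cost is a protocol amendment with Sponsor approval and IRB review (protocol 14.1), and some extra AE entries at visits where AEs are already assessed. SAP 2.1.4.1 can stay as written.

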#### Re-consent criteria

In case of a confirmed diagnosis of MS relapse (as defined in the protocol, Appendix C), **or** in case of an increase in EDSS of 1.0 points or more, sustained for at least 3 months, during the study, the following actions will be taken:

1. The subject will be reminded of the current approved MS medications/treatments and the opportunity to terminate the study and be treated with an approved MS medication.
2. The subject will be requested to re-sign an informed consent form if he/she chooses to continue to participate in the study, in the same treatment assignment.

Subjects enrolled into the study will be closely monitored through the study course by the Sponsor's personnel as well as by an external independent data monitoring committee (DSMB) in order to ensure subjects' welfare.

Investigators must obtain expert evaluations of brain MRI images of subjects with suspected opportunistic CNS infections including PML.

## 10.8 SERIOUS ADVERSE EVENTS

---

### 10.8.1 DEFINITIONS OF SERIOUS ADVERSE EVENTS

---

The definitions of serious adverse events (SAEs) are given below. The principal investigator is responsible for ensuring that all staff involved in the trial are familiar with the content of this section.

An SAE or reaction is defined as any untoward medical occurrence that:

- Results in death, is immediately life-threatening,
- Requires at least a 24-hour in-patient hospitalization or prolongation of existing hospitalization,
- Results in persistent or significant disability/incapacity, and/or
- Causes a congenital anomaly/birth defect.

Medical and scientific judgment should be exercised in deciding whether expedited reporting is appropriate in other situations, such as important medical events that may not be immediately life-threatening or result in death or hospitalization, but may jeopardize the patient or may require intervention to prevent one of the other outcomes listed in the previous definition. These should also usually be considered serious. Examples of such events are intensive treatment in an emergency room or at home for allergic bronchospasm; blood dyscrasias or convulsions that do not result in hospitalization; or development of drug dependency or drug abuse.

A SUSAR is defined as a suspected unexpected SAE, and SUSAR reporting is encompassed within SAE reporting guidelines as defined in this section.

Treatment within or admission to the following facilities is not considered to meet the criteria of "in-patient hospitalization" (although if any other SAE criteria are met, the event must still be treated as an SAE and immediately reported):

- Emergency Department or Emergency Room
- Outpatient or same-day surgery units

- Observation or short-stay unit
- Rehabilitation facility
- Hospice or skilled nursing facility
- Nursing homes, Custodial care or Respite care facility

Hospitalization during the trial for a pre-planned surgical or medical procedure (one which was planned prior to entry in the trial), does not require reporting as a serious adverse event to the Sponsor.

---

## 10.8.2 SERIOUS ADVERSE EVENT REPORTING BY INVESTIGATORS

---

It is important to distinguish between “serious” and “severe” adverse events, as the terms are not synonymous. Severity is a measure of intensity; however, an AE of severe intensity need not necessarily be considered serious. For example, nausea which persists for several hours may be considered severe nausea, but may not be considered an SAE. On the other hand, a stroke which results in a limited degree of disability may be considered only a mild stroke, but would be considered an SAE. Severity and seriousness should be independently assessed when recording AEs and SAEs on the CRF.

Adverse events classified by the treating investigator as **serious** require expeditious handling and reporting to the Sponsor in order to comply with regulatory requirements. Serious adverse events may occur at any time from the signing of the informed consent form through the 30-day follow-up period after the last trial treatment. Sponsor or designee must be notified of all SAEs, regardless of causality, within 24 hours of the first knowledge of the event by the treating physician or research personnel.

**To report an SAE, see the appropriate SAE CRF page.**

All SAEs and medically confirmed deaths (regardless of causality assessment) occurring on trial treatment or within 30 days of last trial treatment must be reported to the sponsor as SAEs within the CRF and followed until resolution (with autopsy report if applicable).

Deaths occurring within 30 days after last trial treatment that are deemed ‘possibly’ or ‘probably’ related to ublituximab must be reported as SAEs within the CRF (with an autopsy report if available).

Deaths occurring within 30 days after last trial treatment and not attributed to trial treatment (e.g., disease progression) need not be reported in an expeditious manner to the Sponsor, but can simply be captured on the appropriate CRF as an SAE (death).

The investigator must review and sign off on the SAE data on the SAE report. The SAE will be reported to the Sponsor (or Sponsor designee) as outlined in the Safety Monitoring Plan.

If an SAE is reported to the sponsor or designee via fax, the same information must be entered on the CRF within 24 hours (1 business day). The SAE transmission should be confirmed by the site personnel submitting the report.

Follow-up information for SAEs and information on non-serious AEs that become serious should also be reported to the sponsor or designee as soon as it is available; these reports should be submitted using the appropriate CRF. The detailed SAE reporting process will be provided to the sites in the Safety Monitoring Plan.

Investigators must report SAEs and follow-up information to their responsible Institutional Review Board (IRBs)/Independent Ethics Committee according to the policies of the responsible IRB (Research Ethics Committee).

## 10.9 SPONSOR SAE REPORTING REQUIREMENTS

---

Sponsor is responsible for reporting relevant SAEs to the competent authority, other applicable regulatory authorities, and participating investigators, in accordance with ICH guidelines, FDA regulations, and/or local regulatory requirements.

Sponsor is responsible for reporting unexpected fatal or life-threatening events associated with the use of the trial drugs to the regulatory agencies and competent authorities via telephone or fax within 7 calendar days after being notified of the event. The Sponsor will report all related but unexpected SAEs including non-death/non-life-threatening related but unexpected SAEs associated with the use of the trial medications to the FDA, investigators, and central IRBs by a written safety report within 15 calendar days of notification. Investigators using local IRBs are responsible for sending written safety reports for these events to their IRBs within 15 calendar days.

## 10.10 RECORDING OF ADVERSE EVENTS AND SERIOUS ADVERSE EVENTS

---

Investigators should use correct medical terminology/concepts when recording AEs or SAEs on the SAE Report Forms and AE CRF. Avoid colloquialisms and abbreviations.

All AEs, including those that meet SAE reporting criteria, should be recorded on the AE CRF; AEs that meet the definition of an SAE should additionally be reported.

## 10.11 DIAGNOSIS VS. SIGNS AND SYMPTOMS

---

All AEs should be recorded individually in the patient's own words (verbatim) unless, in the opinion of the Principal Investigator or designated physician, the AEs constitute components of a recognized condition, disease, or syndrome. In the latter case, the condition, disease, or syndrome should be named rather than each individual sign or symptom. If a constellation of signs and/or symptoms cannot be medically characterized as a single diagnosis or syndrome at the time of reporting, each individual event should be recorded as an AE or SAE as appropriate on the relevant form(s) (SAE Report Form and/or AE CRF). If a diagnosis is subsequently established, it should be reported, as follow-up information is available. If a diagnosis is determined subsequent to the reporting of the constellation of symptoms, the signs/symptoms should be updated to reflect the diagnosis.

